Open-Label Dose-Escalation Period: The open-label dose-escalation period will be 8 weeks in duration and will allow each subject to receive three dose levels of ATR-101 (i.e., 250 mg twice daily (BID), 500 mg BID,

and 1000 mg BID). The 250 mg and 500 mg BID dose levels will each be used for 2 weeks, and the 1000 mg BID dose level will be used for 4 weeks.

- Study Days 1-14: At Visit T1, all subjects will be assigned to take the same starting dose of ATR-101, 250 mg BID, at the beginning of the open-label dose-escalation period. Twenty-four-hour UFCs will be assessed on Days 13 and 14 (collections start on Days 13 and 14, respectively, and finish on Days 14 and 15, respectively).
- Study Days 15-28: At Visit T2, all subjects will be assigned to take the next higher dose of ATR-101, 500 mg BID. Twenty-four-hour UFCs will be assessed on Days 27 and 28 (collections start on Days 27 and 28, respectively, and finish on Days 28 and 29, respectively).
- Study Days 29-56: At Visit T3, all subjects will be assigned to take the next higher dose of ATR-101, 1000 mg BID. Twenty-four-hour UFCs will be assessed on Days 41, 42, 50, 51, and 56 (collections start on Days 41, 42, 50, 51, and 56, respectively, and finish on Days 42, 43, 51, 52, and 57, respectively).

At any time, the ATR-101 dose may be down-titrated as needed for safety reasons at the discretion of the Investigator. There will be no wash-out period between the open-label dose-escalation period and either the double-blind randomized withdrawal period or the additional open-label dosing period.

Double-blind Randomized Withdrawal Period: The double-blind randomized withdrawal period will be up to 4 weeks in duration. A subject is eligible to enter the double-blind randomized withdrawal period if the mean of the Day 50 and Day 51 (“mean Day 50/51”) 24-hr UFCs meets at least one of the following randomization criteria:

- 24-hr UFC \leq ULN
- 24-hr UFC \leq 50% relative to the baseline value

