Eligible subjects will be randomized in a 1:1 ratio to receive either ATR-101 at the same dose level on which they achieved the mean Day 50/51 24-hr UFC \leq ULN (or \leq 50% of their baseline value) or matching placebo. Subjects will continue in the double-blind randomized withdrawal period for 4 weeks or until their mean Day 64/65 24-hr UFC is $> 1.3 \times$ ULN and has also increased by $> 50\%$ relative to their mean Day 50/51 24-hr UFC, whichever comes first. Subjects who are not eligible to be randomized will enter the Additional Open-Label Dosing Period instead of the Double Blind Randomized Withdrawal Period (see below).

- Study Days 57-70: Twenty-four-hour UFCs will be collected on Days 64 and 65 (collections start on Days 64 and 65, respectively, and finish on Days 65 and 66, respectively). At the time of Visit R2 (Day 71), if the mean Day 64/65 24-hr UFC result is available and is $> 1.3 \times$ ULN, and has also increased by $> 50\%$ relative to the mean Day 50/51 24-hr UFC, the subject will complete the End-of-Treatment (EoT) visit (Visit R3) instead of Visit R2 and may then be started on another agent at the discretion of his or her physician. Otherwise, the subject will continue in the double-blind, randomized withdrawal period.
- Study Days 71-85: Twenty-four-hour UFCs will be collected on Days 79 and 84 (collections start on Days 79 and 84, respectively, and finish on Days 80 and 85, respectively). The EoT visit (Visit R3) will be completed on Day 85. Note: if the mean Day 64/65 24-hr UFC was not available at the time of Visit R2, but subsequently is found to meet criteria for study completion, the EoT visit should be performed as soon as practicable, rather than on Day 85. Additionally, if the Day 79 or Day 84 24-hr UFC is $>$ ULN, after completion of the EoT visit (Visit R3) the subject may begin treatment with another agent at the discretion of his or her physician.

Additional Open-Label Dosing Period: The additional open-label dosing period will be 4 weeks in duration. A subject is eligible to enter the additional open-label dosing period if they do not meet any of the randomization criteria described in the above section.

Eligible subjects will be assigned to take ATR-101 1000 mg BID (or a lower dose if needed for safety, at the discretion of the Investigator). Subjects will continue in the additional open-label dosing period for 4 weeks.

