3.1.3. Double-blind Randomized Withdrawal Period

The double-blind randomized withdrawal period will be up to 4 weeks in duration. A subject is eligible to enter the double-blind randomized withdrawal period if the mean of the Day 50 and Day 51 (“mean Day 50/51”) 24-hr UFCs meets at least one of the following randomization criteria:

- 24-hr UFC \leq ULN
- 24-hr UFC \leq 50% relative to the baseline value

Eligible subjects will be randomized in a 1:1 ratio to receive either ATR-101 at the same dose level being used at the completion of the open-label dose-escalation period (expected to be 1000 mg BID) or matching placebo. Subjects will continue in the double-blind randomized withdrawal period for 4 weeks or until their mean Day 64/65 24-hr UFC is $> 1.3 \times$ ULN and has also increased by $> 50\%$ relative to their mean Day 50/51 24-hr UFC, whichever comes first. Subjects who are not eligible to be randomized will enter the Additional Open-Label Dosing Period instead of the Double Blind Randomized Withdrawal Period (see below).

- **Study Days 57-70:** Twenty-four-hour UFCs will be collected on Days 64 and 65 (collections start on Days 64 and 65, respectively, and finish on Days 65 and 66, respectively). At the time of Visit R2 (Day 71), if the mean Day 64/65 24-hr UFC result is available and is $> 1.3 \times$ ULN, and has also increased by $> 50\%$ relative to the mean Day 50/51 24-hr UFC, the subject will complete the End-of-Treatment (EoT) visit (Visit R3) instead of Visit R2 and may then be started on another agent at the discretion of his or her physician. Otherwise, the subject will continue in the double-blind, randomized withdrawal period.
- **Study Days 71-85:** Twenty-four-hour UFCs will be collected on Days 79 and 84 (collections start on Days 79 and 84, respectively, and finish on Days 80 and 85, respectively). The EoT visit (Visit R3) will be completed on Day 85. Note: if the mean Day 64/65 24-hr UFC was not available at the time of Visit R2, but subsequently is found to meet criteria for study completion, the EoT visit should be performed as soon as practicable, rather than on Day 85. Additionally, if the Day 79 or Day 84 24-hr UFC is $>$ ULN, after completion of the EoT visit (Visit R3) the subject may begin treatment with another agent at the discretion of his or her physician.

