3.5. Treatment Assignment

There are a total of 3 dose levels for ATR-101 during the open-label dose-escalation period:

- 250 mg BID
- 500 mg BID
- 1000 mg BID

All enrolled subjects will be assigned to take the same starting dose of ATR-101, 250 mg BID. Dose escalation to the next higher dose of ATR-101, 500 mg BID, will occur at Visit T2. Further dose escalation to the next higher dose of ATR-101, 1000 mg BID, will occur at Visit T3.

A subject may enter the double-blind randomized withdrawal period if the mean Day 50/51 24-hr UFC is \leq ULN or \leq 50% relative to the baseline value. Such subjects will be randomized 1:1 to receive either ATR-101 at the same dose level on which they achieved the mean Day 50/51 24-hr UFC \leq ULN (or \leq 50% of their baseline value) (expected to be 1000 mg BID) or matching placebo in a double-blinded manner.

Subjects who do not meet any of the randomization criteria will enter the additional open-label dosing period and receive ATR-101 1000 mg BID.

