5.8. Randomization and Blinding

After the open-label dose-escalation period, subjects whose mean Day 50/51 24-hr UFC level is \leq ULN or \leq 50% relative to their baseline value will undergo a placebo-controlled, double-blind randomized withdrawal from ATR-101 in which they will be randomized either to continue ATR-101 or placebo. Randomization will be stratified by baseline 24-hr UFC level (calculated as the mean of all 24-hr UFC levels obtained within the 28 days prior to enrollment into the open-label dose-escalation period).

Subjects will continue on the dose of ATR-101 on which they achieved the mean Day 50/51 24-hr UFC \leq ULN (or \leq 50% of their baseline value) or a matching placebo. The matching placebo tablets for the ATR-101 500-mg tablets will maintain double-blind status. Subjects will be administered ATR-101 and/or placebo tablets BID as described in Section 5.5.

The following personnel will be unblinded as to the exact content of investigational treatments (i.e., the randomization code) during the double-blind randomized withdrawal period:

- Personnel analyzing the PK samples

The randomization list will be kept in a secure location until after database lock at the end of the study. However, the study drug assignment will be available if unblinding is required for an SAE. The procedures for emergency unblinding are provided in Appendix 5.

Subjects will be assigned to one of two 24-hr UFC strata. Strata will be assigned by the IVRS/IWRS system according to the baseline 24-hr UFC value, calculated as the mean of all 24-hr UFC levels obtained within the 28 days prior to enrollment into the open-label dose-escalation period:

- Stratum I: 1.3 to $< 4 \times$ ULN
- Stratum II: 4 to $10 \times$ ULN

Enrollment into a particular stratum may be limited to ensure the inclusion of subjects in both strata.

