7.3. Double-blind Randomized Withdrawal Period

Subjects whose mean Day 50/51 24-hr UFC level is \leq ULN or \leq 50% of their baseline value are eligible to enter the 4-week double-blind randomized withdrawal period. (Subjects who do not meet either of these randomization criteria will instead enter an additional 4-week open-label dosing period, described in Section 7.4.) Subjects entering the randomized withdrawal period will be randomized in a 1:1 ratio either to continue to receive ATR-101 at the dose at which they achieved mean Day 50/51 24-hr UFC \leq ULN or \leq 50% of their baseline value (expected to be 1000 mg BID), or matching placebo. Randomization will be stratified by baseline 24-hr UFC level (calculated as the mean of all 24-hr UFC levels obtained within the 28 days prior to enrollment into the open-label dose-escalation period). Subjects' 24-hr UFC levels will be followed during this period to determine the efficacy of ATR-101 in maintaining lowered levels compared to placebo.

During the double-blind randomized withdrawal period, the Investigator should assess the mean Day 64/65 24-hr UFC result as soon as possible to determine whether the subject meets criteria for study completion. Subjects are considered to have completed the study during the double-blind randomized withdrawal period when their mean Day 64/65 24-hr UFC level is $> 1.3 \times$ ULN and has also increased by $> 50\%$ relative to their mean Day 50/51 24-hr UFC level, or if they reach Visit R3 without meeting these criteria. When subjects are found to have completed the study, they should return to the study site immediately for Visit R3.

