- Contact IVRS/IWRS to randomize the subject into the double-blind randomized withdrawal period and obtain study drug assignment.
- Dispense blinded study drug and instruct the subject on self-administration of study drug orally with food BID.
- Have the subject eat breakfast.
- Ask the subject to self-administer study drug with a nonalcoholic beverage (except grapefruit juice) while at the study site. Record the exact time of study drug administration.
- Provide instructions to the subject regarding 24-hr urine samples and saliva samples to be collected at home prior to the next visit (Section 7.3.2).
- Schedule the next study visit (Visit R2) so that the blood hormone sample collections for that visit will occur as close to 8 AM (08:00) as practicable and between 6-10 AM (06:00-10:00).
- Remind the subjects that they will need to record the approximate time of their evening study drug dose prior to their next visit.
- Remind the subjects that on the morning of their next visit, they should wait to take their morning dose of study drug until directed by site personnel at the study site.

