12. APPENDICES

APPENDIX 1. STUDY SCHEDULE

Table 6: Study Schedule, Screening and Open-Label Dose-Escalation Periods

	Screening	Open-Label Dose-Escalation Period														
		Study Day: [†] -56 to -1	1	13	14	15	27	28	29	41	42	43	50	51	52	56
Visit: [†]	S1	T1			T2			T3			tel					
Study Drug Dose: [*]	None	ATR-101 250 mg BID		ATR-101 500 mg BID		ATR-101 1000 mg BID										
Informed Consent	X															
Inclusion/Exclusion	X	X														
Medical History & Demographics	X															
Vital Signs, Height and Weight ^a	X	X			X			X								
Physical Examination ^b	X	X			X			X								
12-lead ECG	X															
Hematology & Chemistry	X	X			X			X								
PT, aPTT, INR, Insulin, HbA1c, Lipids ^c	X															
Serology (HBsAg, HCV, HIV)	X															
Blood Hormone Levels ^d	X	X			X			X								
Plasma PK ^e		X			X			X								
Serum/Urine Pregnancy Test ^f	X	X			X			X								
Urinalysis/Urine Drug Screen ^g	X	X														
Begin 24-Hr Urine Collection ^h	XX ^h		X	X		X	X		X	X		X	X		X	
Early Morning Salivary Cortisol ⁱ	XX ⁱ		X	X		X	X		X	X		X	X		X	
Late Night Salivary Cortisol ⁱ	XX ⁱ		X	X		X	X		X	X		X	X		X	
Submit Completed 24-Hr Urine Collections and Saliva Collections to Central Lab ^{h,i}	XX ^{h,i}				X			X			X			X		
Enrollment into Open-Label Dose-Escalation Period		X														
Dispense Study Drug		X			X			X								
Collect Study Drug/Assess Compliance					X			X								
Prior and Concomitant Medications	X	X			X			X			X					
Adverse Events ^k		X			X			X			X					

Footnotes are located at the end of Appendix 1.

Table 7: Study Schedule, Double-Blind Randomized Withdrawal Period and Follow-Up Period

Study Day: [†]	Double-Blind Randomized Withdrawal Period								Follow-Up Period			
	57	64	65	66	71	79	80	84	85	92 [^]	93 [^]	98 [^]
Visit: [†]	R1				R2				R3 EoT/ ET			F1 EoS
Study Drug Dose: [*]	ATR-101 1000 mg BID or Placebo								None			
Inclusion/Exclusion	X [§]											
Vital Signs and Weight	X				X				X			X [^]
Physical Examination ^b	X				X				X			X [^]
12-lead ECG	X								X			
Hematology & Chemistry	X				X				X			X [^]
PT, aPTT, INR, Insulin, HbA1c, Lipids ^c	X								X			
Blood Hormone Levels ^d	X				X				X			X [^]
Plasma PK ^e	X				X				X			
Serum/Urine Pregnancy Test ^f	X				X				X			X [^]
Urinalysis	X								X			
Begin 24-Hr Urine Collection ^h		X	X			X		X		X [^]		
Early Morning Salivary Cortisol ⁱ		X	X			X		X				
Late Night Salivary Cortisol ⁱ		X	X			X		X				

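### Section 3.1.3 and four other parts of the protocol give different rules for the ATR-101 dose at randomization, and they disagree for a subject whose dose is lowered between the Day 50/51 collections and Visit R1

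*Protocol*

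**What the plan says.** The dose for the active arm in the randomized withdrawal period is stated in five places in the text of the protocol.

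- Section 3.1.3: "ATR-101 at the same dose level being used at the completion of the open-label dose-escalation period (expected to be 1000 mg BID").
- Synopsis, Double-blind Randomized Withdrawal Period: "randomized in a 1:1 ratio to receive either ATR-101 at the same dose level on which they achieved the mean Day 50/51" UFC criterion.
- Section 3.5: "Such subjects will be randomized 1:1 to receive either ATR-101 at the same dose level on which they achieved the mean Day 50/51" UFC criterion.
- Section 5.8: "Subjects will continue on the dose of ATR-101 on which they achieved the mean Day 50/51 24-hr UFC" criterion.
- Section 7.3: "to continue to receive ATR-101 at the dose at which they achieved mean Day 50/51 24-hr UFC" criterion.

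The study drug dose row of Table 7 in Appendix 1 reads only "ATR-101 1000 mg BID or Placebo".

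On dose changes, the Synopsis, Section 3.1.2 and Section 7.2 all state: "At any time, the ATR-101 dose may be down-titrated as needed for safety reasons at the discretion of the Investigator". Section 3.7 also allows reductions in the open-label period and asks that they be discussed with the Medical Monitor.

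At Visit R1 (Section 7.3.1) the site is told: "Contact IVRS/IWRS to randomize the subject into the double-blind randomized withdrawal period and obtain study drug assignment".

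**The concern.** Section 3.1.3 ties the active dose to the end of the open-label dose-escalation period. The other four statements tie it to the Day 50/51 collections, several days earlier. If the dose is lowered for safety between those two points, one subject has two different doses under the same protocol.

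Three things depend on the answer.

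- **Drug assignment.** The IVRS/IWRS issues the assignment at Visit R1 and needs a single rule. Read literally, the Day 50/51 wording sends an active-arm subject back, under blind, to a dose that had just been lowered for safety. The Section 3.1.3 wording carries the lowered dose forward.
- **What randomization changes.** Under Section 3.1.3 the dose of an active-arm subject does not change at randomization. Under the other wording it does, in exactly these subjects. The early-completion rule compares the mean Day 64/65 UFC with the mean Day 50/51 UFC, so whether both values reflect the same active dose also depends on the rule.
- **Matching tablets.** By the Synopsis, 1000 mg is two 500-mg tablets and 500 mg is one. The number of placebo tablets needed to match therefore follows from the same rule.

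**Working it through.** No figure in the protocol needs to be reproduced. The check sets the rules side by side and counts the days in which they can diverge.

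**Step 1: the rules by case**

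| Subject's dose history | Section 3.1.3 | Synopsis, 3.5, 5.8, 7.3 | Agree? |
|---|---|---|---|
| 1000 mg BID throughout Days 29-56 | 1000 mg BID | 1000 mg BID | Yes |
| Lowered before Day 50, then unchanged | Lowered dose | Lowered dose | Yes |
| Lowered after the Day 50/51 collections, before Visit R1 | Lowered dose | Earlier, higher dose | No |

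Only the third row is in conflict. No section gives an order of precedence.

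**Step 2: can the third row occur?** Yes. Reductions are allowed at any time in the open-label dose-escalation period (Synopsis, 3.1.2, 7.2), and the gap lies inside that period. Sections 3.1.3, 3.5 and 7.3 call 1000 mg BID only the expected dose, so they allow for others.

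**Step 3: length of the gap.** Count from the day the Day 51 collection finishes (start day + 1, Section 3.1.2) to the day before Visit R1:

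gap in days = day of Visit R1 − day the second collection finishes

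- Target dates: 57 − 52 = 5 days (Days 52 to 56).
- Window of ± 2 days on both (Section 6.1): longest 59 − 50 = 9 days; shortest 55 − 54 = 1 day.
- Window of + 2 days on both (Section 7 and the footnotes to Appendix 1): longest 59 − 52 = 7 days; shortest 57 − 54 = 3 days.

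The protocol states both windows, so both are shown. Section 6.1 also allows later assessments to be re-anchored, so neither range is a firm bound. The 5-day figure is the useful one.

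**Step 4: how would a reduction arise in the gap?** Table 6 schedules no adverse-event assessment between the Day 43 telephone visit and Visit R1. A reduction in the gap would therefore follow an unscheduled contact.

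**Step 5: how many subjects?** About 16 are to be enrolled (Section 3.4), only those meeting the Day 50/51 criterion are randomized, and the allocation is 1:1. The protocol gives neither a down-titration rate nor an expected number randomized, so no percentage can be derived. The number of active-arm subjects affected would be small and may be zero.

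**The case against.** The strongest reply is that one dose was intended and described in two ways. Sections 5.8 and 7.3 speak of continuing on a dose, which presupposes that it has not changed. Sections 3.1.3, 3.5 and 7.3 share the same expected dose. The sections closest to operations, 3.5 and 5.8, agree with each other, so the outlier is a single sentence in the design overview. A recent reduction would hardly go unnoticed: dose adjustments should be discussed with the Medical Monitor (3.7), the Investigator may withdraw the subject (4.3), and at Visit R1 the site records adverse events and collects study drug before randomizing (7.3.1). The IVRS/IWRS specification is not among the documents and may already hold one rule. Table 7 is weak evidence, since Tables 6 and 8 also show 1000 mg BID where the text allows a lower dose. Finally, with so few subjects at risk, the matter is minor.

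Much of this stands. The case is uncommon, the safeguards make an unnoticed return to the higher dose less likely, and the dose row of Table 7 looks like a planned dose that favours neither rule. The analysis group is not affected either, because efficacy is analysed as randomized (9.3).

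The contradiction remains. Reading continuation as assuming an unchanged dose leaves the changed-dose case without an answer. None of the safeguards says which dose is assigned. An IVRS/IWRS built to one rule would still contradict part of the protocol.

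**Conclusion.** The inconsistency is real. For an active-arm subject lowered between the Day 50/51 collections and Visit R1, Section 3.1.3 and the other four statements cannot both be followed. For every subject whose dose is unchanged after Day 50/51 they give the same dose.

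The scope is narrow: a nominal gap of 5 days and few subjects, perhaps none. This rests on the target visit dates and on reductions occurring only through unscheduled contact. Endpoint definition, eligibility for randomization, analysis group and sample size are untouched. The point still deserves correction because it concerns an operative drug-assignment rule, it arises just when a dose has been lowered for safety, and it is cheap to settle. This review takes no view on which rule is right.

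**What to change.** Reconcile the Synopsis, Sections 3.1.3, 3.5, 5.8 and 7.3, and the dose row of Table 7 to one dose-assignment rule. The rule should state what applies when the dose was lowered between the Day 50/51 collections and Visit R1, and the IVRS/IWRS, including the matching placebo tablet count, should be programmed or checked against it. The choice of rule belongs to the sponsor and the Medical Monitor.

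The cost is protocol wording and an IVRS/IWRS check. The sample size and visit schedule do not change.

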3.1.4. Additional Open-Label Dosing Period

The additional open-label dosing period will be 4 weeks in duration. A subject is eligible to enter the additional open-label dosing period if they do not meet any of the randomization criteria described in the above section.

Eligible subjects will be assigned to take ATR-101 1000 mg BID (or a lower dose if needed for safety, at the discretion of the Investigator). Subjects will continue in the additional open-label dosing period for 4 weeks.

- Study Days 57-70: Twenty-four-hour UFCs will be collected on Days 69 and 70 (collections start on Days 69 and 70, and finish on Days 70 and 71, respectively).
- Study Days 71-85: Twenty-four-hour UFCs will be collected on Days 79 and 84 (collections start on Days 79 and 84, respectively, and finish on Days 80 and 85, respectively). The EoT visit (Visit A3) will be completed on Day 85. Note: if the Day 79 or Day 84 24-hr UFC is > ULN, after completion of the EoT visit (Visit A3) the subject may begin treatment with another agent at the discretion of his or her physician.

3.1.5. Follow-up Period

During the follow-up period, subjects will continue to be monitored for safety. Subjects whose most recent 24-hr UFC is \leq ULN will have a follow-up visit (Visit F1/End-of-Study, EoS; this is the same as the end of trial) at the study site 2 weeks after their ET/EoT visit. Subjects whose most recent 24-hr UFC is $>$ ULN will have a follow-up telephone visit instead of a study site visit.

- Study Days 86-98: If the Day 79 24-hr UFC is \leq ULN, a follow-up visit (Visit F1) at the study site will be scheduled for Day 98, 2 weeks after the EoT visit. This visit will consist largely of safety assessments. Subjects whose Day 84 24-hr UFC is also \leq ULN will begin a 24-hr urine collection on Day 92 and finish on Day 93. If the Day 79, Day 84 or Day 92 24-hr UFC is $>$ ULN, a telephone visit will be conducted on Day 98 instead of a study site visit (in case of discrepant results, the latest result should be used). If the Day 92 24-hr UFC result is unknown at the time the Day 98 visit is due, the subject will proceed with having the Day 98 visit at the study site.
- Subjects whose Day 92 24-hr UFC is \leq ULN should continue to be followed up and have morning serum ACTH and 24-hr UFC assessed every 2-4 weeks until their 24-hr UFC is $>$ ULN or until the Investigator and the Medical Monitor agree that the subject is stable.

Throughout the course of the study, safety evaluations will include assessment of AEs, concomitant medications, clinical laboratory tests, vital signs, physical examinations (PEs) and 12-lead electrocardiograms (ECGs).

A detailed schedule of study assessments is presented in [Appendix 1](#).

